2.2.6.7 IMRT Evaluations and Data Collection

2.2.6.7.1 IMRT Simulation and Planning

A CT scan as described in Section 2.2.4 must be done post implantation for **BOTH Groups**. The baseline radiation therapy (XRT) plan, and the core lab simulation, will be based on this CT. Planning must follow the contouring instructions (provided separately). Planning must occur after imaging and no later than 21 days post marking/implantation. The post-implantation simulation will be based on the planning images.

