2.2.6.7.2 IMRT Treatments

In general, *for both groups*, IMRT (XRT) must start no more than 24 days after marking/ implantation. Sites will perform a weekly positioning verification using Cone beam or low dose CT scan. For the *Balloon Group*, scan results will also be used to verify balloon spacing of at least 10 mm. Subjects will receive IMRT based on the sites' dose-fractionation schedule. The following data will be captured for *both groups* during the last day of a weekly visit, for as many weeks as the treatment lasts:

IMRT Data Collection:

This data should be captured once per week on the last day of that weeks' treatment sessions during active IMRT treatment.

Weekly

- For *Balloon Group* verification of spacing status as at least 10 mm (from prostate to rectum);
- Changes in medications;
- Expanded Prostate Cancer Index (EPIC) assessment (done once at mid-point assuming the treatment plan exceeds one month (4 weeks));
- Perineal access site healing status (until healed) and
- Adverse events as defined by Sections 2.3.6 and 2.3.7 of this Protocol.

Last XRT Visit

- CT scan taken as described in Section 2.2.4 for the *Balloon*;
- Changes in medications;
- Expanded Prostate Cancer Index (EPIC) assessment and
- Adverse events as defined by Sections 2.3.6 and 2.3.7 of this Protocol.

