2.2.8 DATA COLLECTION SUMMARY

Time Point	Pre-implantation ¹	Implantation	Post- Implantation ⁴	IMRT ⁵ Treatments	IMRT Follow-up
Informed Consent	X ¹				
Medical History & Physical Examination ¹	X ¹				
AUA Symptom Score	X ¹				
Broad Spectrum Antibiotics	X ²				
Randomization	X ³				
Medications	X ¹			Х	Х
CT as per Section 2.2.4 as indicated ⁶	Х		X	Х	Х
Perineal Healing Status (until healed)				Х	
EPIC Assessment ⁷	Х			Х	Х
Adverse Events		As Needed			
Study Completion/ Termination		As Needed			

Study windows:

- 1. Pre-implantation evaluations.
- 2. Broad-spectrum antibiotics must be started 2 days prior to implantation and continued for a total of 5 days.
- 3. Randomization may occur up to 30 days prior to implantation to allow for facility set up and must occur prior to the pre-implantation CT scan.
- 4. The Post-implantation period begins at discharge from the facility and extends to the first IMRT treatment.
- 5. IMRT treatments must start no more than 24 days after marking/ implantation and data will be collect weekly on the last day of that week's visits.
- 6. CT is taken for the *Balloon Group* up to 30 days pre-implantation and post-implantation, at the last XRT visit and at the 6-month F/U visit. Additionally, CT may be taken in the *Balloon Group* at 12 months if remnants of the balloon remain at 6 months. A CT will be taken in the *Control Group* post-implantation.
- 7. EPIC is taken at baseline, at mid XRT treatment (assuming the treatment plan is for greater than one month) on last XRT day and at every follow-up visit thereafter.

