While it is advantageous to treat prostate cancer with the highest feasible dose, it is currently avoided by most therapy centers due to the fact that higher dosage to the prostate will eventually result in higher dosage to the rectum. Inserting the balloon in situ between the prostate and the rectum will enable admission of higher dosage whether as total (accumulative) or per session (hypofractionation) or both, potentially reducing acute and late and chronic rectal toxicity.

The rectal toxicity of conventional radiation therapy (XRT) and even the current focused XRT machinery and methods (3D- CRT, IMRT and IGRT), and the hypofractionation trend, potentially can be reduced as lesser radiation at any given dose to the prostate will eventually reach the rectum. Grade 2-3 late and chronic toxicity ranges from 5 to 20 % and more (in particular with hypofractionation). The adverse event rate (Grade 1 events) for the Augmenix SpaceOAR was 34% (DEN140030).

The potential reduction of radiation to the rectum at any given radiation dose to the prostate will potentially reduce acute rectal toxicity, which in turn may reduce the late and chronic rectal toxicity.

The assumed potential risk of using the BioProtect Balloon Implant Systemis mainly the potential risk for rectal perforation and from injury during the implantation procedure. It should be noted however, that unlike the late complications associated with high-dose radiation that are chronic and may take years for resolution, this potential risk is temporary and reversible. Nevertheless, the potential risk of rectal perforation is mitigated by the following actions:

- 1. The entire procedure will be done with the guidance of Trans Rectal Ultra Sound (TRUS); and the user will be a well-trained urologist or physician that is familiar with the brachytherapy transperineal approach using TRUS.
- 2. The user will be well trained by the company to the specific implantation procedure with relation to the anatomy. This will be done by thorough reading of the IFU, simulating the implantation on a phantom model using TRUS, explanation of videos showing the phantom simulation and human real case simulation, and supervising the initial cases as needed, by a company trained physician.
- 3. The delivery system uses a spinal needle type, which is blunt at the tip.

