#### 7.1 Table 1. Data Collection Summary

Time Point	Pre-implantation 	Implantation	Post- Implantation 	IMRT Treatments 	IMRT Follow-up 
Informed Consent	X 				
Medical History & Physical Examination 	X 				
AUA Symptom Score	X 				
Broad Spectrum Antibiotics	X 				
Randomization	X 				
Medications 	X 			Х	Х
CT 	X		Х	Х	Х
Perineal Healing Status (until healed) 				Х	
EPIC Assessment 	X			Х	Х
Adverse Events		As Needed			
Study Completion/ Termination		As Needed			

Study windows:

- 1. Pre-implantation evaluations.
- 2. Broad-spectrum antibiotics must be started 2 days prior to implantation and continued for a total of 5 days.
- 3. Randomization may occur up to 30 days prior to implantation to allow for facility set up and must occur prior to the pre-implantation CT scan.
- 4. The Post-implantation period begins at discharge from the facility and extends to the first IMRT treatment.
- 5. IMRT treatments must start no more than 24 days after marking/implantation and data will be collected weekly on the last day of that week's visits.
- 6. Medications, perineal healing status (until healed), and verification of spacing status (*ProSpace Group*) are captured once per week during active IMRT treatment on the last day of that week's treatment sessions.
- 7. CT will be taken for the *ProSpace Group* up to 30 days pre-implantation and post-implantation, at the last XRT visit and at the 6-month follow-up visit. Additionally, CT may be taken in the *ProSpace Group* at 12 months if remnants of the balloon remain at 6 months. CT will be taken in the *Control Group* post-implantation.
- 8. EPIC will be taken at baseline, at mid XRT treatment (assuming the treatment plan is for greater than one month), on last XRT day, and at every follow-up visit thereafter.
- 9. The subject will be seen at 6 months (± 2 weeks) and every 6 months thereafter (± 4 weeks) from the time of marking/implantation until the last subject has completed 6 months of follow-up.

Statistical Analysis Dlan	Client/Project	BioProtect BP-007
Statistical Analysis Flan	Version and Date	V2 05-DEC-2021

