#### Secondary Safety Endpoint #2: EPIC Scores

An additional secondary safety endpoint concerns the degree of all GU acute toxicity as determined by the Expanded Prostate Cancer Index Composite (EPIC). The version used in this study was the EPIC-26 short form. EPIC scores range from 0 to 100 (transformed from Likert scale responses), with higher scores indicative of better functioning. For each of four EPIC domains (Urinary Incontinence, Urinary Irritative, Bowel, and Sexual), the analysis of the EPIC endpoint will evaluate change in EPIC score over time.

<sup>3 Wei JT, Dunn RL, Litwin MS, Sandler HM, Sanda MG. Development and validation of the expanded prostate cancer index composite (EPIC) for comprehensive assessment of health-related quality of life in men with prostate cancer. Urology. 2000;56(6):899-905.

Statistical Analysis Dlan	Client/Project	BioProtect BP-007
Statistical Allalysis Flan	Version and Date	V2 05-DEC-2021

The domain scores will be summarized descriptively by visit and group along with the change from baseline. Non-parametric Rank-Sum tests will be used to compare change from baseline between groups for each domain at the IMRT midpoint and IMRT final visit.

In addition, for each domain, change from baseline in EPIC score over the course of the study will be evaluated using a mixed model. The independent variables will include visit, treatment group and visitby-treatment group interaction as factors, continuous baseline EPIC score as a covariate and Subject as a random effect. The model will used with an unstructured covariance matrix. In case it fails to converge, a compound symmetry covariance matrix will be used. Least Squares Means will be used to estimate between-group differences for each visit. Type III tests for the factors will be provided.

In addition, change in EPIC score from Screening to the end of IMRT will be analyzed using a separate analysis. The timing of the final IMRT visit is not fixed across subjects, and therefore, cannot be considered as part of the mixed model described above.

This endpoint will be analyzed using the following regression:

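### Mid-treatment EPIC is skipped for plans of 4 weeks or less, so the midpoint comparison covers long-course men only, and nothing requires plan length to be fixed before randomisation

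*Protocol*

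**What the plan says.** Protocol 2.2.6.7.2 lists EPIC among the weekly IMRT data as "done once at mid-point assuming the treatment plan exceeds one month (4 weeks". Note 7 of Protocol 2.2.8 carries the same condition, and SAP 7.1 Table 1, note 8, schedules the form "at mid XRT treatment (assuming the treatment plan is for greater than one month". EPIC on the last day of radiotherapy has no such condition.

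SAP 10.3.5.1 nevertheless plans a between-arm test at both times: "Non-parametric Rank-Sum tests will be used to compare change from baseline between groups for each domain at the IMRT midpoint and IMRT final visit". Tables 14.2.6.2, 14.2.7.2, 14.2.8.2 and 14.2.9.2 report it. A mixed model by visit is also planned, and the SAP keeps the final IMRT visit out of that model because its timing varies between subjects. Outside the primary endpoints, SAP 10.1 uses available data with no imputation. Neither document has a rule for men who have no midpoint form by design.

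On timing, Protocol 2.2.8 states "Randomization may occur up to 30 days prior to implantation", and Protocol 2.2.6.7.1 states "Planning must occur after imaging and no later than 21 days post marking/implantation". On the source of the schedule, Protocol 2.2.6.7.2 states "Subjects will receive IMRT based on the sites' dose-fractionation schedule". Protocol 2.2.4 limits fractionation only through biological equivalence to a stated dose range.

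**The concern.** A between-arm test is protected by randomisation only if membership of the analysed set does not depend on anything the assignment could influence. Here membership depends on plan length. The plan follows randomisation by up to 30 + 21 = 51 days. It is made on a CT in which the balloon can be seen, by a radiation oncologist who may also have done the implantation (Protocol 2.2.5.1 and 2.2.6.5). No stratification by site or schedule is named (Protocol 2.2.3). The protocol's benefit-risk text, between 2.3.6.2 and 2.3.8, says the device would permit higher dose "whether as total (accumulative) or per session (hypofractionation) or both", so the documents themselves connect the balloon with shorter courses.

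At stake is one of the two on-treatment EPIC comparisons. The mixed model is touched as well. The SAP does not list that model's visits, but with the final IMRT visit excluded, the midpoint is the only on-treatment EPIC it could contain. Short-course men would then contribute no on-treatment score to it, and course length is not a term in the model.

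**Working it through.** **1. The plan's own figures.** No power or precision is stated for EPIC. The sample size reproduces: 204/0.92 = 221.7, so 222 enrolled, with 136 balloon and 68 control evaluable. The co-primary powers also reproduce: efficacy 94.9% (exact binomial, success at 113 or more of 136), safety 85.1% (Farrington-Manning), product 0.949 × 0.851 = 0.808. The counts 136 and 68 are used below.

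**2. Who lacks a midpoint form.** Protocol 2.2.4 refers to 78-81 Gy in 1.8-2 Gy fractions. That is 78/2 = 39 to 81/1.8 = 45 fractions. At an assumed 5 fractions per week this is 39/5 = 7.8 to 45/5 = 9 weeks. A 4-week plan holds 4 × 5 = 20 fractions. So only hypofractionated plans lose the form, and the equivalence wording permits them. The share of such plans is not given.

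**3. Case A: same schedule in both arms of a site.** The analysed subset is then defined independently of arm, and the test stays valid within it. The detectable difference in SD units (two-sided 0.05, 80% power) is (1.960 + 0.842) × √(1/n_balloon + 1/n_control).

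| Assumed short-plan share, both arms | Balloon / control left | Detectable difference (SD) |
|---|---|---|
| 0% | 136 / 68 | 0.42 |
| 10% | 122 / 61 | 0.44 |
| 20% | 109 / 54 | 0.47 |
| 30% | 95 / 48 | 0.50 |
| 50% | 68 / 34 | 0.59 |

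At 20%, for example: 2.802 × √(1/108.8 + 1/54.4) = 2.802 × 0.166 = 0.47.

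**4. Case B: shares differ by arm.** Suppose 20% to 40% of balloon men and 10% of control men have short plans (assumed).

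- Men left: 136 × 0.8 = 109 to 136 × 0.6 = 82 balloon, and 68 × 0.9 = 61 control. The loss is 17% to 30% of 204.
- SE ratio = √[(1/n_balloon + 1/n_control) / (1/136 + 1/68)] = 1.076 to 1.139, an increase of 8% to 14%.
- If short-course men differ from long-course men by d points in both arms, dropping them shifts the arm difference by (share difference) × d. With d of 3 to 8 points (assumed), the shift is 0.1 × 3 = 0.3 to 0.3 × 8 = 2.4 points. Its sign follows the sign of d.

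**5. False-positive rate of the midpoint test.** Simulated Rank-Sum test at nominal 0.05: 4,000 runs per setting, 136 against 68, no true arm difference, short-plan men omitted. Shares and correlations are assumptions.

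| Short plans, balloon / control | Unrelated to EPIC change | Correlation 0.3 | Correlation 0.5 |
|---|---|---|---|
| 20% / 20% | 0.050 | 0.052 | 0.052 |
| 30% / 10% | 0.048 | 0.075 | 0.174 |
| 40% / 10% | 0.047 | 0.128 | 0.280 |
| 50% / 10% | 0.053 | 0.176 | 0.402 |

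The rate moves off 0.05 only when the shares differ and plan length is related to EPIC change. In these runs short plans went to men with better change, so the estimate moved against the balloon (by 0.085 SD at 30%/10% and correlation 0.3). The opposite relation would reverse the sign.

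**The case against.** Four arguments stand on the other side.

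- **The schedule may belong to the site.** A reader might infer that plan length is chosen for each man after unblinded implantation, so that the midpoint sets are no longer randomised. The documents do not say so. Fractionation is tied to the site's schedule, and Protocol 2.2.4 places it among site requirements. Building a plan on the post-implantation CT does not mean that the number of fractions is decided then. This stands: selection by arm is possible and unaddressed, not shown.
- **No direction is documented.** A reader might also infer bias in favour of the balloon, because the benefit-risk text links hypofractionation to more toxicity. That sentence concerns late and chronic toxicity, in a passage about the rectum. It says nothing about mid-treatment scores in urinary, bowel and sexual domains. The remark that the device would permit hypofractionation is an argument for the device, not an instruction to vary schedules by arm. This stands too.
- **Acute toxicity is measured in everyone elsewhere.** Last-day EPIC is collected whatever the course length, with its own Rank-Sum test and baseline-adjusted regression. It is also the EPIC test named for a labelling claim in Protocol 2.3.3. This limits the reach of the point but does not repair the midpoint test.
- **A midpoint form in every man mixes elapsed times.** Half of a 4-week course is week 2, while half of a 7.8- to 9-week course is about week 4. This is true, but the SAP already compares the arms at a final visit whose timing differs by subject. It is a reason to report course length, not to omit the men.

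**Conclusion.** The point holds as a secondary-endpoint weakness that should be corrected. The collection rule removes men from the midpoint comparison by a characteristic that neither document requires to be fixed before randomisation, and the SAP does not allow for it.

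The size depends on facts the documents do not give. If schedules are the same for both arms within a site, the cost is precision and scope: the detectable difference goes from 0.42 SD to 0.47 SD at an assumed 20% short plans, and the result speaks only for men with plans longer than 4 weeks. If schedules differ by arm and course length is related to EPIC change, the test is biased. Under the assumed settings its false-positive rate runs from 0.075 to 0.402, in a direction that cannot be stated. Neither co-primary endpoint is affected, nor is the last-day EPIC test.

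**What to change.** - Delete the 4-week condition in Protocol 2.2.6.7.2, Protocol 2.2.8 note 7 and SAP 7.1 Table 1 note 8.
- Collect EPIC in every man of both groups at the weekly visit nearest half of his planned fractions, provided this is a different visit from the last XRT visit.
- Record the intended schedule for each man before randomisation.
- Run the midpoint Rank-Sum tests, and the mixed model where it uses the midpoint, on all men in the group as randomised.

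If collection is already complete, give course length and midpoint denominators by arm alongside Tables 14.2.6.2 to 14.2.9.2. SAP 10.3.6.2 already summarises IMRT length in weeks, but only beside perineal healing. Label the midpoint comparison as restricted to men with plans longer than 4 weeks, and present last-day EPIC as the all-subject acute comparison.

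The cost is one extra EPIC-26 form in short-course men at a weekly data-collection visit they already attend, one field recorded before randomisation, and wording edits in three places. No change to any treatment schedule is proposed.

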2.2.6.8 Follow-up Visits

The subject will be seen at 6 months (± 2 weeks) and every 6 months thereafter (± 4 weeks) from the time of marking/balloon implantation until the last subject has completed 6 months of follow-up. Data collected will include:

- At the 6 month visit CT scan taken in the same position as for the IMRT Plan and as described in Section 2.2.4 for the *Balloon Group*;
- Changes in medications;
- Expanded Prostate Cancer Index (EPIC) assessment and
- Adverse events as defined by Sections 2.3.6 and 2.3.7 of this Protocol.

The six (6) month visit will be the last visit conducted for primary analysis.

2.2.7 STUDY COMPLETION, TERMINATION OR LOSS TO FOLLOW-UP

All subjects are expected to remain in the study for at least 6 months following implantation of the balloon. Subjects who complete their 6 month visit prior to the last study subject's completion of the 6 month visit will continue to be followed every 6 months until the last subject enrolled has completed the 6 month evaluation.

Subjects may be withdrawn from a clinical study early due to withdrawal of Informed Consent, loss to follow-up, Investigator medical decision, Regulatory Body decision, an adverse event which would render subsequent data invalid for the purposes of demonstrating the safety and effectiveness of the device, or even death. Any premature termination from the study will be documented, including the primary reason for withdrawal.

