2.2.5 STUDY DESIGN

2.2.5.1 OVERALL STUDY DESIGN

This study will be a prospective, multi-center, randomized, double-arm, single blind, concurrently controlled study to assess the safety and efficacy of the BioProtect Balloon Implant System in prostate cancer subjects undergoing radiotherapy by means of IMRT.

Subjects will be randomized in a 2:1 ratio (balloon implantation:control) to receive either IMRT +marking + balloon implantation or IMRT +marking. The balloon will be inserted during the same session of the marking.

Subjects will be blinded to study assignments. It is not practical to blind the surgeon or surgeon's staff since they will participate in the insertion procedure and/or be responsible for

maintaining source documentation. Additionally, the core lab cannot be blinded since the balloon will be visible on the CT images.

All subjects enrolled in the study will be included in an "intent-to-treat" analysis regardless of failure to complete the required follow-up examinations. Subjects will be considered enrolled in the study for the purposes of an intent-to-treat analysis only after they have provided Informed Consent and have been randomized. Preliminary data will be captured for subjects excluded intraoperatively, documenting the reason(s) for exclusion. It is anticipated that very few, if any, subjects will be excluded intraoperatively. Sites will maintain a log of screening failures, documenting the reason for failure. Additionally, subjects who are randomized but not implanted (e.g., due to an adverse event that prevents or significantly delays their radiation treatment) may be removed from the study. Such removals will be documented and reported appropriately. Subjects who are screening failures or who are removed from the study prior to implantation will be excluded from analysis.

This study will utilize a core laboratory for analysis of CT images. Post implantation CT images for the *Balloon Group* will be compared to pre-implantation images to demonstrate the change in distance and potential for rectal protection provided by the balloon.

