2.2.6.5 BALLOON AND MARKER IMPLANTATION, EVALUATIONS AND DATA COLLECTION

Prior to the implantation procedure subjects in *BOTH Groups* will receive an enema per center standard for marking the prostate and may receive medication to relieve anxiety. This should be recorded in the medications eData file.

For the *Balloon Group*, urethral catheterization is recommended at the beginning of the implantation procedure to drain the bladder and aid the positioning of the balloon. At the end of the procedure (or per local standards) the catheter should be removed.

The term "Investigator" refers to the radiation oncologist who is in charge of the planning and the IMRT treatments. However, the implantation procedure may be done by the radiation oncologist, or by a urologist who is proficient in performing transperineal procedures via transrectal Ultrasound guidance. Additionally, Investigator performing the simulation may be done by an oncologist, a medical physist, or other qualified person

This protocol requires prostate marking for *all subjects* in both study arms (*Control and Balloon Groups*). Therefore, this visit must be carried out at the location where the marking is usually done by the respective center (OR, Brachytherapy suit, etc.) by the same physician that will be inserting the balloon.

For *both groups*, the marking *MUST* be done transperineally (not transrectally). This technique will avoid potential puncture of the balloon by a marker in the *Balloon Group* and minimize the potential for data bias due to different insertion techniques.

Note: the enema must employ the same protocol for prepping the rectum as would be employed if the marking was being performed transrectally.

The insertion of the balloon will be done using a free-hand approach with the aid of a trans rectal US. Any form of anesthesia may be utilized at the discretion of the implanting physician. However, whenever possible, each center should remain consistent with the choice of anesthesia to avoid potential differences in temporary post-operative sequelae. The subject may receive local, spinal or general anesthesia. However, the subject should be at least relaxed medically to prevent accidental movement.

For Balloon Group subjects, the balloon implantation will be performed after the marking, and will be performed by a urologist/physician who will be trained by the company for balloon insertion.

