#### 10.3.4.1 Co-Primary Safety Endpoint and Analysis

#### 10.3.4.1.1 Primary Safety Endpoint

The adverse events qualifying as primary safety events will be determined through adjudication by the CEC. The primary safety endpoint is based on the occurrence of one or more adverse event as follows, as indicated on the CEC CRF:

- Event is indicated to be a Grade 1 or greater rectal event lasting at least 2 days through the first 183 days (6 months) and
- Event meets one of the relatedness classifications:
  - Event is indicated to possible, probably, or definitely device-related;
  - Event is related to marking or
  - Event is related to the balloon implantation procedure.

Note that events related to anesthesia or to the use of a foley catheter will not be considered marking or implantation procedure-related.

Subjects will be counted as having an event if one occurs anytime through Day 183 (6 months) from the marking date or as not having an event if they record no events and are followed through at least Day 169 (6 month minus 14 days) from the marking date. Subjects who terminate the study before Day 169 and did not experience the AE of interest will be considered missing from the PP population and not included in the primary safety analysis. The impact of these subjects will be evaluated in a sensitivity analysis for the primary safety endpoint as described below.

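### The protocol allows withdrawal from the study for an adverse event or a medical decision without further AE follow-up, and the SAP then leaves those without a qualifying event before Day 169 out of the primary safety analysis

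*Protocol*

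**What the plan says.** Protocol 2.2.7 first sets the expectation: "All subjects are expected to remain in the study for at least 6 months following implantation of the balloon". It then lists grounds for leaving early: "Subjects may be withdrawn from a clinical study early due to withdrawal of Informed Consent, loss to follow-up, Investigator medical decision, Regulatory Body decision", followed by "an adverse event which would render subsequent data invalid for the purposes of demonstrating the safety and effectiveness of the device", and death. The reason must be documented. The section gives no criteria for the medical-decision ground, does not say who decides that later data are invalid, and does not ask for AE collection after withdrawal.

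SAP 10.3.4.1.1 defines the qualifying event, as adjudicated by the CEC. The first condition is "Event is indicated to be a Grade 1 or greater rectal event lasting at least 2 days through the first 183 days (6 months) and"; the event must also be related to the device, the marking or the balloon implantation. A subject with such an event through Day 183 is counted as an event. A subject without one is counted as event-free only if followed to at least Day 169. For the rest: "Subjects who terminate the study before Day 169 and did not experience the AE of interest will be considered missing from the PP population". They are not in the primary safety analysis, and their impact is referred to sensitivity analysis.

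On blinding, Protocol 2.2.5.1 says "It is not practical to blind the surgeon or surgeon's staff", and also that "the core lab cannot be blinded since the balloon will be visible on the CT images". Protocol 2.2.6.5 says that the investigator "refers to the radiation oncologist who is in charge of the planning and the IMRT treatments".

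**The concern.** For a safety endpoint counted through Day 183, AE data collected after an earlier AE are part of the outcome, so they cannot be invalid for showing safety. The balloon is implanted once, so there is no continuing device treatment whose stopping would explain the end of follow-up.

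The subjects who can be lost are those withdrawn with a non-qualifying AE, or by medical decision. Under the SAP definition, a non-rectal device event is an example: migration, or erosion into the bladder, both within the risks listed in Protocol 2.3.6.1. Such a subject leaves numerator and denominator. If he would later have had a rectal event of at least 2 days adjudicated as device-, marking- or implantation-related, nobody records it.

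Device and balloon-implantation events cannot occur in controls, and the surgeon and staff know the arm. The loss can therefore fall more on the balloon arm, and on subjects at higher risk there. That would lower the observed balloon rate and favour a finding of non-inferiority on a co-primary endpoint.

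**Working it through.** **The plan's own figure.** Inputs from Protocol 2.3.4.1 and 2.3.4.4 and SAP 6: 136 balloon and 68 control evaluable, event rates 19% and 21%, margin 0.15, one-sided 0.025, Farrington-Manning test. The statistic is

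z = (p_B − p_C − 0.15) / SE0, with SE0 = √[r_B(1−r_B)/n_B + r_C(1−r_C)/n_C],

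where r_B and r_C are the rates fitted under r_B − r_C = 0.15. At the design rates r_B = 0.2717, r_C = 0.1217 and SE0 = 0.0550. The unrestricted SE is √(0.19×0.81/136 + 0.21×0.79/68) = 0.0598. Power = Φ[(0.17 − 1.96×0.0550)/0.0598] = 0.851, which reproduces the stated 85%. Enrolment also reproduces: 204/0.92 = 221.7, rounded up to 222.

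**Planned drop-outs.** 148 − 136 = 12 balloon and 74 − 68 = 6 control.

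**Result at the planned rates.** 0.19×136 ≈ 26 and 0.21×68 ≈ 14. For 26/136 v 14/68 the difference is −1.5 points, SE0 = 0.0549, z = −3.002, p = 0.0013.

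**Restoring both arms to 148 and 74.** The documents give no withdrawal rate by reason, so the number of drop-outs who would have had a qualifying event is an assumption and is varied here.

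| Balloon drop-outs with event (of 12) | Control (of 6) | Counts | Difference, points | z | One-sided p |
|---|---|---|---|---|---|
| 2 | 1 | 28/148 v 15/74 | −1.4 | −3.125 | 0.0009 |
| 6 | 1 | 32/148 v 15/74 | +1.4 | −2.536 | 0.0056 |
| 8 | 0 | 34/148 v 14/74 | +4.1 | −2.031 | 0.021 |
| 9 | 0 | 35/148 v 14/74 | +4.7 | −1.892 | 0.029 |
| 10 | 1 | 36/148 v 15/74 | +4.1 | −1.979 | 0.024 |
| 11 | 1 | 37/148 v 15/74 | +4.7 | −1.844 | 0.033 |
| 12 | 2 | 38/148 v 16/74 | +4.1 | −1.932 | 0.027 |
| 12 | 3 | 38/148 v 17/74 | +2.7 | −2.149 | 0.016 |

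The first row is roughly the planned rate among drop-outs, and nothing changes. Non-inferiority is lost at 9 of 12 balloon events if no control drop-out has an event, at 11 if one has, and at 12 if two have. With three or more control events it is not lost at all.

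**Near the margin.** Suppose the true rates are 36% and 21%, so that the balloon is exactly 15 points worse. With everyone kept (148/74), exact enumeration gives a one-sided type I error of 0.027. If w balloon subjects who would all have had an event are dropped and no control is, the balloon rate among those left is (0.36×148 − w)/(148 − w): 0.351, 0.342 and 0.333 for w = 2, 4 and 6. The type I error becomes 0.037, 0.050 and 0.068. This is a one-sided worst case, but it takes few subjects.

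**The case against.** Much is already in place. SAP 10.3.4.1.3 plans a tipping-point analysis over every combination of outcomes in both arms, and Kaplan-Meier estimates at Day 183 that use partial follow-up. SAP 10.3.1 summarises reasons for discontinuation by arm, and Table 14.3.3.1 lists AEs that lead to discontinuation, so a lopsided loss would be visible. This stands, but it has limits. These analyses show fragility; they cannot supply outcomes that were not collected. The tipping point has no criterion for failure, and Kaplan-Meier assumes that censoring is unrelated to risk, which withdrawal for an AE may violate.

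Three stronger readings are tempting and are not supported:

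- A reader might infer that unblinded investigators remove subjects because of AEs. Protocol 2.2.7 ties the AE ground to data becoming invalid and does not say who applies it; only the medical-decision ground is the investigator's. Protocol 2.2.5.1 names the surgeon, the surgeon's staff and the core lab as unblinded. That the planning radiation oncologist also knows the arm is a reasonable inference from the CT, but it is not stated.
- A reader might infer that subjects with safety events vanish. Those with a qualifying event stay counted however early they leave. A later rectal event due to IMRT alone would not have counted under the SAP. A non-rectal implantation event may even qualify under Protocol 2.2.2.3 and 2.3.4.1, whose wording is not clearly limited to rectal events; that mismatch is a separate matter.
- A reader might add back balloon subjects only and conclude that 10 events overturn the result (36/146 v 14/68, p=0.027). That leaves out the 6 planned control drop-outs. With them restored, the threshold is 9 if none has an event, and 10 is not enough if one has.

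**Conclusion.** The gap is real. Followed as written, the two documents allow AE collection to end because of an AE or a medical decision, and then take those subjects out of the primary safety test. The bias can favour the balloon.

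The size cannot be given, since the 8% drop-out is not split by reason. If the two arms lose 12 and 6 subjects as planned and the observed rates are near 19% and 21%, the decision changes only in a severe case: about 9 or more of the 12 balloon drop-outs with events and almost no control drop-out with one. Short of that, the conclusion holds at those rates but the estimated difference is biased: from −1.5 points observed to +1.4 with 6 balloon events and 1 control event. If the true difference lies near the margin, a few informative losses are enough to raise the type I error. The documents do not show that such losses will happen or that they will be one-sided. The case for acting is that the remedy is cheap.

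**What to change.** In Protocol 2.2.7, remove the AE ground based on later data being invalid as a reason to end data collection. State that any marked or implanted subject withdrawn for an AE or by medical decision stays in AE follow-up through Day 183, with telephone contact acceptable, unless he withdraws consent, is lost to follow-up, dies, or a regulatory body orders follow-up to stop. AEs collected in this way go to the CEC and count in the primary safety analysis in SAP 10.3.4.1.

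Optionally, in SAP 10.3.4.1.3, single out the scenario that counts withdrawals before Day 169 because of an AE as events in both arms. This is essentially one scenario of the tipping-point analysis already planned, so it helps the reader but does not replace continued follow-up.

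The change concerns data collection, not clinical management. It costs a short amendment and a few extra contacts with subjects who would otherwise have left; the 6-month visit is already scheduled and the reason for withdrawal already recorded. The sponsor must accept that the balloon event rate may come out less favourable.
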